Total body muscle mass will be assessed directly by the D₃-creatine dilution method (27). Low muscle mass measured by this method has been associated with slower walking speed, lower SPPB score, and more falls in older men (27). The D₃-creatine dilution method involves a participant ingesting a capsule containing the 60-mg dose of stable isotope-labeled creatine (D₃-creatine), and then providing a fasting morning urine sample 72–144 hours (3–6 days) later. To minimize variability in this muscle mass measurement, participants will be asked not to eat foods containing creatine or creatinine (animal products) after their mid-day meal on the day prior to these urine collections on visits 0 and 12 months. A handout will be provided to guide participants in what they should and should not eat on these two occasions. Urine D₃-creatinine, unlabeled creatinine, and creatine are measured using high performance liquid chromatography and tandem mass spectroscopy; these measures are then included in an algorithm to determine total body creatine pool size and thus skeletal muscle mass (39). The doses will be prepared by Greenpark Pharmaceuticals in Houston, TX. The urine samples will be de-identified and sent to [name] laboratory at U.C. Berkeley for analysis. [name] will be blinded to treatment group and sequence (baseline, 12 mo) during the analyses.

Biochemical measurements

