Secondary aims - With 4 measurements (baseline, 2, 6, and 12 months), we will test whether the change over time is linear with use of linear models with random effects. The observed pattern of change in ALM over time will give an indication of the potential long-term benefit (or lack thereof) of anamorelin treatment. A significance level of 0.05 will be used.

The findings from secondary (and exploratory) analyses will be used for hypothesis generation, rather than to draw conclusions.

Exploratory aims – Exploratory outcomes will be analyzed as described above. For those with more than two measurements, the pattern of change will be analyzed as described above for ALM.

The primary analyses will follow intention-to-treat principles. The intent to treat population will include all subjects who had 1 or more visits after visit 0 (baseline). We will also perform per protocol analyses, in which subjects who develop clinical conditions during the study that influence the study outcomes (i.e., started treatment on an osteoporosis drug or glucocorticoids) or with selected protocol deviations will be excluded. Data will be diagnosed to evaluate validity of model assumptions. Assumptions of normality and homoscedasticity will be evaluated in these models and appropriate variable transformations will be applied if needed to satisfy model assumptions. If model assumptions do not hold for the linear mixed models, robust standard errors will be used. An exploratory per-protocol analysis will also be performed.

Safety and tolerability measures will be summarized for each treatment group based on clinical symptoms and circulating levels of glucose and ALT/AST. Adherence will be assessed by intake diary and pill counts.

K. Withdrawal from the study

Participants can go permanently “off study” only for withdrawal of consent, defined as no longer wishing to participate in all aspects of the trial. The PI may also withdraw participants for safety reasons. Participants can be off of study pills (non-adherent) but remain in the study and return for scheduled follow-up visits. Participants who are instructed by their doctor to gain weight during the study will not be withdrawn from the study.

PROTECTION OF HUMAN SUBJECTS

a. Materials and potential risks

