The FDA will be kept informed of the most current IRB approved protocol throughout this study so that the IND can be updated. We will send annual reports to the FDA that are linked in timing and content to the Continuing Review information sent annually to the IRB. We will send a summary of the study results to the FDA at the end of the study.

Record retention - Subjects' records will be retained for the timeframe described in the record retention policy of the "[SOP – Records Retention Timeframe – Investigators.](#)"

Vulnerable Populations: This study does not include vulnerable populations.

Alternatives - Subjects may choose not to participate in the study. Their participation is voluntary. Everything done in this study is being done for research.

Withdrawal - Subjects are free to stop their participation at any time for any reason. Participants will be considered lost to follow-up if we are unable to reach them by telephone or email after trying weekly for 10 weeks. At that point, no further attempts will be made to contact them. Should subjects decide to withdraw from the study, the study measurements made before their withdrawal may be included in the scientific analysis and publication of the study results. To withdraw from the study, subjects can contact [name] at [contact]. [name] may also end a subject's participation in the study at any time in order to protect his/her safety or to maintain the smooth conduct of the study.

c. Potential benefits to subjects

This study is not designed to benefit individual subjects. Screening lab results will be made available to the subjects. Subjects will have the option to receive copies of their screening spine and hip DXA scans two to three weeks after their visit. Intra-study laboratory tests will be made for research only and will not be shared with participants. If any adverse medical conditions are discovered during the study, subjects will be notified and referred to their doctor.

Risk/benefit assessment

The risks incurred are minimal relative to the potential benefit of gaining information about one's health.

Payment plan

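### Contact stops for good after 10 unanswered weeks, with no renewed attempt before the only follow-up measurement of the primary endpoint, and one ground for removing participants conflicts with section K

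*Combined protocol and SAP*

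**What the plan says.** **Unreachable participants.** The Withdrawal paragraph under Protection of human subjects states: "Participants will be considered lost to follow-up if we are unable to reach them by telephone or email after trying weekly for 10 weeks". It continues: "At that point, no further attempts will be made to contact them".

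**Removal by the study.** The same paragraph lets one named individual end participation "in order to protect his/her safety or to maintain the smooth conduct of the study".

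**Section K (Withdrawal from the study).** Participants go permanently off study "only for withdrawal of consent, defined as no longer wishing to participate in all aspects of the trial". K then adds a second route: "The PI may also withdraw participants for safety reasons". It also keeps people who stop treatment: "Participants can be off of study pills (non-adherent) but remain in the study and return for scheduled follow-up visits".

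**Primary measurement.** The schedule in section B shows D3-creatine dosing at day -3 and day 361 only. The D3-creatine text in section F refers to diet instructions "on the day prior to these urine collections on visits 0 and 12 months". No interim value is taken.

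**Analysis and size.** Section A plans 32 enrolled and 24 completers. Section J compares 12-month change by a two-sample t-test. It defines the intention-to-treat set as everyone with at least one visit after baseline, and gives no missing-data method for the primary test.

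**The concern.** There are two separate issues.

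First, the contact rule takes no account of when the primary outcome is collected. A participant who cannot be reached in the first half of the year is not approached again, although the month-12 tracer and urine sample may be months away and the person has never declined them. Because there is no interim D3-creatine value, a missed month-12 visit leaves no primary change score. If no post-baseline visit was attended either, the person also drops out of the intention-to-treat set as section J defines it. Those who go silent may not be a random sample, and the primary t-test has no stated way of handling their absence.

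Second, the smooth-conduct ground is neither consent nor safety and is not defined. Two sections of one protocol therefore give different answers on who may be removed after randomisation. The answer determines whose month-12 outcome is collected.

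**Working it through.** **1. Timing of the contact rule.** Ten weeks is 70 days, and 70 / 30.4 = 2.3 months. Closure month = start of failed attempts + 2.3. Time remaining = 12 - closure month.

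| Attempts start (month) | Attempts end (month) | Months left to the primary measurement |
|---|---|---|
| 2 | 4.3 | 7.7 |
| 4 | 6.3 | 5.7 |
| 6 | 8.3 | 3.7 |
| 8 | 10.3 | 1.7 |
| after 9.7 | after 12.0 | none; the rule has no effect |

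The month-2 row applies only if the 2-month visit itself is missed. After an attended 2-month visit the next planned contact is the 4-month call. Read literally, someone closed at month 4.3 or 6.3 would not receive the calls that section B schedules at months 8 and 10.

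**2. The two withdrawal texts side by side.**

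| Situation | Section K | Withdrawal paragraph | Relation |
|---|---|---|---|
| Consent withdrawn | off study | free to stop | agree |
| Safety | PI may withdraw | may be ended | agree |
| Off pills | stays, attends visits | not addressed | no direct clash |
| Cannot be reached | not addressed | contact stops after 10 weeks | adds to K |
| Smooth conduct | not a ground | may be ended | conflict |

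**3. Related text on safety stops.** Under Protection against risks, a participant with repeated fasting glucose of at least 200 mg/dl stops study pills and continues with measurements for the intention-to-treat analysis. Under Stopping rules, the same finding ends participation in the study. These two statements also disagree on whether the month-12 outcome is collected.

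**4. The plan's sample-size figure.** Inputs from section I: SD of change 1.84 kg, target difference 2.28 kg, 12 per group. Assumed: two-sided test, alpha 0.05 (stated in section J under the secondary aims) and 80% power (none is stated for the primary aim).

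- Standard error of the difference = SD x sqrt(2/n). Power comes from the noncentral t distribution with 2n - 2 degrees of freedom and noncentrality 2.28 / standard error.
- n = 12: 1.84 x sqrt(2/12) = 0.751; 2.28 / 0.751 = 3.04. Power is 82.7% and the detectable difference at 80% power is 2.20 kg. This is below 2.28 kg, so the plan's figure is reproduced.
- n = 11: 1.84 x sqrt(2/11) = 0.785; 2.28 / 0.785 = 2.91. Power is 78.9% and the detectable difference is 2.31 kg, above 2.28 kg.
- Planned attrition: (32 - 24) / 32 = 25%.

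**5. Sensitivity to the number of completers (illustration only).**

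| Completers | Power at 2.28 kg | Detectable difference, 80% power |
|---|---|---|
| 26 | 85.8% | 2.11 kg |
| 24 (planned) | 82.7% | 2.20 kg |
| 23 | 80.8% | 2.26 kg |
| 22 | 78.9% | 2.31 kg |
| 20 | 74.6% | 2.44 kg |

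The documents do not say how many participants the contact rule or the smooth-conduct ground would affect, so no row can be attributed to either.

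**The case against.** The best defence is that ten weekly attempts by two channels is a real effort. It is supported by scheduled calls, by the instruction to report hospitalisations and changes in health, and by a $300 payment after the 12-month visits. The plan already budgets for 8 losses. All of this stands, and it limits how often the rule would matter. It does not explain why someone who has not withdrawn consent is not approached once more when the primary measurement falls due.

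Several stronger readings are tempting, and the documents do not support them.

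- *The 10-week rule contradicts section K.* K is silent on people who cannot be reached. The rule ends outreach. It does not say that the person is withdrawn or would be refused a month-12 visit.
- *Primary values will be needlessly lost.* There is no count of people affected, nor of how many would attend if contacted again.
- *Staff may drop non-adherent participants.* The power belongs to one named individual, and section K expressly retains non-adherent participants. The fault is an undefined ground that could be read to reach them.
- *The rule pushes the trial below its target power.* The 2.31 kg figure describes the loss of any one participant per arm beyond the planned 24, whatever the cause.
- *Losses will differ by arm.* This is possible, but nothing in the documents shows it.

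**Conclusion.** The point holds in two parts. The contact rule forgoes an inexpensive chance to recover the primary outcome from participants who go silent before about month 9.7. The smooth-conduct ground contradicts section K's limits on removal and sits badly with its retention of non-adherent participants.

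The size of the loss cannot be estimated. The sensitivity figures show only that the margin is thin: with 23 completers power stays just above 80%, and with 22 it falls just below. They rest on the plan's SD of 1.84 kg and on the assumed two-sided alpha of 0.05 and 80% power. The risk of selective loss does not depend on those assumptions, but it remains a risk and not a finding. The change should be made because it is cheap and protects the only follow-up measurement of the primary endpoint.

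**What to change.** 1. **Contact rule.** Keep the 10-week rule for routine calls. Add that, unless consent was withdrawn, the participant is contacted once more by call, email and letter before the month-12 tracer date, and is offered the month-12 tracer dose, urine sample and DXA.
2. **Removal ground.** Delete the smooth-conduct ground for randomised participants, or limit it so that it does not end outcome collection. The Withdrawal paragraph would then agree with section K.
3. **Safety stops.** In the same edit, reconcile Protection against risks with Stopping rules on whether participants stopped for safety reasons remain in study measurements. Which clinical rule applies is for the investigators to decide; this review does not choose it.

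**Cost.** A few sentences in the protocol, with matching consent wording where needed, and one contact round for the few people concerned. The study already mails payments, so a letter adds little. The downside is one further contact to people who have been silent. Items 1 and 2 change no dose, treatment or safety rule.
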